7.2. Laboratory Evaluations

Laboratory data collected during the study will be analyzed using qualitative methods. Shift from baseline to worst post-baseline assessment and Grade 3 or higher lab abnormalities will be summarized for the Safety Analysis Set and will include data collected up to the last dose of andecaliximab plus 30 days for subjects who have permanently discontinued andecaliximab or up to the last dose of nivolumab plus 5 months for subjects who have permanently discontinued nivolumab. Severity grade for lab abnormalities are defined by CTCAE 4.03.

Only central lab results will be used in the analyses.

A by-subject listing for laboratory test results will be provided by subject ID number and time point in chronological order for hematology, serum chemistry, urinalysis, coagulation, and thyroid function separately. Values falling outside of the relevant reference range and/or having a severity grade of 1 or higher on the CTCAE severity grade will be flagged in the data listings, as appropriate.

No formal statistical testing is planned.

7.2.1. Graded Laboratory Values

The Gilead Grading Scale for Severity of Adverse Events and Laboratory Abnormalities CTCAE Version 4.03 will be used to assign toxicity grades (0 to 4) to laboratory results for analysis. Grade 0 includes all values that do not meet the criteria for an abnormality of at least Grade 1. For laboratory tests with criteria for both increased and decreased levels, analyses for each direction (ie, increased, decreased) will be presented separately.

7.2.1.1. Treatment-Emergent Laboratory Abnormalities

Treatment-emergent laboratory abnormalities are defined as values that increase at least 1 toxicity grade from baseline at any postbaseline time point, up to and including the date of last dose of andecaliximab plus 30 days or nivolumab plus 5 months for subjects who permanently discontinued study drug, or the last available date in the database snapshot for subjects who were still on treatment at the time of an interim analysis. If the relevant baseline laboratory value is missing, any abnormality of at least Grade 1 observed within the time frame specified above will be considered treatment emergent.

7.2.1.2. Summaries of Laboratory Abnormalities

The following summaries (number and percentage of subjects) for treatment-emergent laboratory abnormalities will be provided by lab test and treatment group; subjects will be categorized according to the most severe postbaseline abnormality grade for a given lab test:

- Graded laboratory abnormalities
- Grade 3 or 4 laboratory abnormalities

A by-subject listing of treatment-emergent Grade 3 or 4 laboratory abnormalities will be provided by subject ID number and time point in chronological order. This listing will include all test results that were collected throughout the study for the lab test of interest, with all applicable severity grades and abnormal flags displayed.

7.2.2. Shifts Relative to the Baseline Value

Shift tables will be presented by showing change in severity grade from baseline to worst post baseline assessment.

7.3. Body Weight and Vital Signs

Descriptive statistics will be provided by treatment group for body weight and vital signs as follows:

- Baseline value
- Values at each postbaseline visit
- Change from baseline at each postbaseline visit

A baseline value will be defined as the last available value collected on or prior to the date/time of first dose of study drug. Change from baseline to a postbaseline visit will be defined as the postbaseline value minus the baseline value.

In the case of multiple values in an analysis window, data will be selected for analysis as described in Section 3.8.3. No formal statistical testing is planned.

A by-subject listing of vital signs and body weight will be provided by subject ID number and time point in chronological order. Body weight will be included in the vital signs listing, if space permits. If not, they will be provided separately.

7.4. Concomitant Medications

Medications collected during the study will be coded using the current version of the [Gilead-modified] World Health Organization (WHO) Drug dictionary.

7.4.1. Prior Medications

A summary of prior medications will not be provided.

7.4.2. Concomitant Medications

Concomitant medications are defined as medications taken while a subject took study drug. Use of concomitant medications will be summarized by Anatomical Therapeutic Chemical (ATC) drug class Level 2 and preferred name using the number and percentage of subjects for each treatment group. A subject reporting the same medication more than once will be counted only once when calculating the number and percentage of subjects who received that medication. The summary will be ordered alphabetically by ATC medical class and then by preferred term in descending overall frequency within each ATC medical class. For drugs with the same frequency, sorting will be done alphabetically.

For the purposes of analysis, any medications with a start date prior to or on the first dosing date of study drug and continued to be taken after the first dosing date, or started after the first dosing date but prior to or on the last dosing date of study drug will be considered concomitant medications. Medications started and stopped on the same day as the first dosing date or the last dosing date of study drug will also be considered concomitant. Medications with a stop date prior to the date of first dosing date of study drug or a start date after the last dosing date of study drug will be excluded from the concomitant medication summary. If a partial stop date is entered, any medication with the month and year (if day is missing) or year (if day and month are missing) prior to the date of first study drug administration will be excluded from the concomitant medication summary. If a partial start date is entered, any medication with the month and year (if day is missing) or year (if day and month are missing) after the study drug stop date will be excluded from the concomitant medication summary. Medications with completely missing start and stop dates will be included in the concomitant medication summary, unless otherwise specified. Summaries will be based on the Safety Analysis Set. No formal statistical testing is planned.

All prior and concomitant medications (other than per-protocol study drugs) will be provided in a by-subject listing sorted by subject ID number and administration date in chronological order.

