3.5.1. Discontinuation Criteria for Nivolumab

In addition to the discontinuation reasons outlined in Section 3.5, please refer to the current nivolumab label or SmPC for your respective region for full discontinuation criteria during treatment with nivolumab.

Nivolumab should also be discontinued for any dosing interruption lasting > 6 weeks with the following exceptions:

- Dosing interruptions to allow for prolonged steroid tapers to manage drug-related AEs are allowed. Prior to re-initiating treatment in a subject with a dosing interruption lasting > 6 weeks, the Sponsor Medical Monitor/Study Director must be consulted. Tumor assessments should continue as per protocol even if dosing is interrupted.
- Dosing interruptions > 6 weeks that occur for non-drug-related reasons may be allowed if approved by the Sponsor Medical Monitor/Study Director. Prior to reinitiating treatment in a subject with a dosing interruption lasting > 6 weeks, the Sponsor Medical Monitor/Study Director must be consulted. Tumor assessments should continue as per protocol even if dosing is interrupted.

If nivolumab therapy is permanently discontinued for any reason, subjects on Treatment Arm A should also permanently discontinue andecaliximab therapy at the same time. Subjects enrolled on Treatment Arm A who discontinue andecaliximab for reasons other than progression may continue nivolumab after consultation with the Sponsor Medical Monitor/Study Director.

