5.4.1. Acceptable Concomitant Medications

All treatments that the investigator considers necessary for a subject's welfare may be administered at the discretion of the investigator in keeping with the community standards of medical care. All concomitant medication will be recorded on the case report form (CRF) including all prescription, over-the-counter (OTC), herbal supplements, and IV medications and fluids. If changes occur during the trial period, documentation of drug dosage, frequency, route, and date may also be included on the CRF.

All concomitant medications received within 30 days before the first dose of trial treatment and 30 days after the last dose of trial treatment should be recorded.

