4.2.1. Duration of Exposure to Study Drug

Total duration of exposure to study drug will be defined as last dosing date minus first dosing date plus 14, regardless of any temporary interruptions in study drug administration, and will be expressed in weeks using up to 1 decimal place (eg, 4.5 weeks). If the last study drug dosing date is missing, the latest date among the study drug end date, clinical visit date, laboratory sample collection date, and vital signs assessment date that occurred during the on-treatment period will be used for subjects included in the final analyses.

The total duration of exposure to study drug will be summarized using descriptive statistics. Summaries will be provided by treatment group for the Safety Analysis Set.

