7.1.5. Treatment-Emergent Adverse Events

7.1.5.1. Definition of Treatment-Emergent Adverse Events

Treatment-emergent adverse events (TEAEs) are defined as both of the following:

- Any AEs with an onset date on or after the study drug start date and up to 30 days after permanent discontinuation of andecaliximab or 5 months after permanent discontinuation of nivolumab
- Any AEs leading to premature discontinuation of andecaliximab or nivolumab

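### The by-arm concomitant-medication summary stops at the last infusion, so immunosuppressants first started for a treatment-ending adverse event will often be missing, contrary to the protocol's safety-summary window

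*SAP*

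**What the plan says.** SAP 7.4.2 defines the scope of the summary: "Concomitant medications are defined as medications taken while a subject took study drug". It then applies date rules, under which any medication with "a start date after the last dosing date of study drug will be excluded from the concomitant medication summary". The result is shown "using the number and percentage of subjects for each treatment group". It is descriptive: "Summaries will be based on the Safety Analysis Set. No formal statistical testing is planned". The section also provides a by-subject listing of prior and concomitant medications.

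Other parts of the plan look past the last dose:

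- SAP 7.1.5.1 counts adverse events as treatment-emergent up to 30 days after andecaliximab or 5 months after nivolumab is permanently stopped. It also counts "Any AEs leading to premature discontinuation of andecaliximab or nivolumab".
- Protocol 8.2.1.2 and 8.6 use the later of the same two limits for the data in the safety summaries; 8.6 specifies that these are by treatment group.
- Protocol 5.4.1 sets the collection period for medications. Its closing limit is "30 days after the last dose of trial treatment should be recorded".
- Protocol 7.3.2.1 requires drugs used to treat a serious adverse event to be entered as concomitant medication.

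Protocol 3.5.1 foresees steroid treatment without permanent discontinuation: "Dosing interruptions to allow for prolonged steroid tapers to manage drug-related AEs are allowed". SAP 7.7 states that the safety analyses do not deviate from the protocol.

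**The concern.** Whether a drug given for toxicity appears in the table depends on whether the subject was dosed again. Suppose two subjects start the same steroid 5 days after an infusion for the same kind of event. One resumes dosing and is counted. The other never does, and is not. Resuming or stopping is itself a tolerability outcome, so the table selects on something that the safety comparison is meant to examine.

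Comparing safety and tolerability between the arms is a secondary objective. According to SAP section 1, the synoptic study report takes only its efficacy analysis from the primary-analysis SAP, so its safety content follows this document. Nothing else visible in the SAP tabulates post-dose steroid or immunosuppressant use by arm. If the arms differ in how often toxicity ends treatment rather than interrupting it, the steroid counts would not be comparable. A reader would have no by-arm figure to correct them with.

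**Working it through.** The plan states no figure here to reproduce. The check applies the date rule to medication start dates and sets the windows side by side.

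**Inputs.** Dosing every 2 weeks (Protocol 3.3). Summary cut-off at the last dosing date (SAP 7.4.2). Minimum medication collection of 30 days after the last dose (Protocol 5.4.1). Safety window of 30 days after andecaliximab or 5 months after nivolumab, whichever is later (Protocol 8.2.1.2 and 8.6). With 30.4375 days per month, the conversion used in SAP 6.2.1, 5 months = 5 × 30.4375 = 152.2 days.

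**Applying the rule.** Days are counted from the last dose of study drug, with nivolumab as the last drug given.

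| Medication start | Within 30-day collection minimum | Adverse event with same onset is treatment-emergent | In by-arm medication summary |
|---|---|---|---|
| Day −7 or 0 | yes | yes | yes |
| Day +1, +7, +14 or +30 | yes | yes | no |
| Day +90 or +150 | no | yes | no |

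**Coverage of new starts after the last dose.** Medication summary 0 days; required collection 30 days; safety window about 152 days. The 30-day minimum covers 30/152.2 = 19.7% of the safety window.

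**Exceptions within SAP 7.4.2.** A medication with both dates completely missing is kept. One with a partial start date is excluded only if the known month and year (or year) falls after the study drug stop date, so a start in the same month as the stop is kept. A subject is counted once per medication, so anyone who took that drug earlier on treatment is already in the table.

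**Which last dose.** Under Protocol 3.5.1, stopping nivolumab also stops andecaliximab in Arm A, but a subject who stops andecaliximab alone may continue nivolumab. SAP 7.4.2 does not say whether the last dosing date is then that of andecaliximab or of either drug. On the second reading, later medications are still counted.

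**How far collection reaches.** Protocol 5.4.1 gives 30 days. The procedures table in Appendix 2 marks adverse events and concomitant medications at the 5-month visit. Its footnote d ends at the 30-day visit or the end-of-study visit, whichever is later. These three do not agree. The 30-day visit is also timed from the last andecaliximab dose (Protocol 6.7), which Arm B never receives.

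**The case against.** An on-treatment definition of concomitant medication is a common convention, and SAP 7.4.2 applies it consistently. Protocol 8.6.1 to 8.6.4 name no medication table. This has force: without the general window in Protocol 8.2.1.2 and 8.6, the choice would be only a matter of definition. But that window covers safety data summarized by arm, SAP 7.4 sits in the safety section, and SAP 7.7 declares no change.

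A reader might also see contradictions with two other passages. In SAP 4.2.1, "Total duration of exposure to study drug will be defined as last dosing date minus first dosing date plus 14"; but this measures exposure, a different quantity. Protocol 5.4.1 is a collection rule, and summarizing less than is collected is not a contradiction. Neither passage carries the point, though 5.4.1 shows that the data for the first 30 days should exist.

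A reader might further infer that the plan hides the toxicity itself. It does not. SAP 7.1.6 tabulates by arm the events leading to discontinuation, Grade 3 or higher events, serious events and deaths. The by-subject listing may also show the later drugs, although the on-drug definition leaves its reach unclear. What is missing is a by-arm count of the treatment those events required.

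The rule is also the same in both arms. It distorts the comparison only if stopping and resuming differ between them, which is not known in advance.

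**Conclusion.** The point stands as an undeclared departure from the protocol's safety-summary window. It leaves a selective gap in one descriptive table and is worth correcting because the correction is cheap. It rests on the 2-weekly schedule, under which treatment for an event that ends dosing will often begin after the final infusion.

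The size in subjects is unknown, since the documents give no count of such events or of drugs started for them. It is tempting to argue that only 1 of the 14 days in a dosing interval is the infusion day, so that about 7% of these courses are kept. The documents do not support that as an estimate. It needs uniform onset, treatment starting on the day of onset, onset always after the last infusion, and no earlier use of the same drug.

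Nor do the documents show that mild events are kept and the worst are lost. An event needing a prolonged steroid taper can be followed by re-dosing under Protocol 3.5.1, and its treatment is then counted.

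**What to change.** - Keep the on-treatment table in SAP 7.4.2.
- Add a by-arm summary of systemic corticosteroids and other immunosuppressants recorded as given for an adverse event, started from first dose through 30 days after the last dose of any study drug. Protocol 5.4.1 already requires medications to be recorded over this period in both arms.
- State that the last dosing date means the later of the two drugs' last doses.
- Extend the summary to the 5-month window only after Protocol 5.4.1, the procedures table and footnote d are reconciled on how long medications are collected. Check at the same time that recording after the last dose is equally complete in Arm B. Otherwise, declare the shorter window in SAP 7.7.

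The cost is some SAP wording and one extra descriptive table. Post-treatment steroid use has to be separated by indication, because Protocol 5.4.2 prohibits no therapy during post-treatment follow-up and some steroids will be supportive care. The data items named in Protocol 5.4.1 do not include the reason for use, so confirm that the case report form captures it. The change concerns reporting only.

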7.5. Electrocardiogram Results

7.5.1. Investigator Electrocardiogram Assessment

A by-subject listing for ECG assessment results will be provided by subject ID number and visit in chronological order.

7.6. Other Safety Measures

No additional safety measures are specified in the protocol.

7.7. Changes From Protocol-Specified Safety Analyses

There are no deviations from the protocol-specified safety analyses.

8. PHARMACOKINETIC (PK) ANALYSES

8.1. PK Sample Collection

PK plasma samples will be collected for Arm A only for andecaliximab PK at 30(\pm 15) min after the end of infusion on Day 1; prior to dosing and 30(\pm 15) min after the end of infusion on Day 1 of Weeks 4, 8, 16, 24, every 3 months thereafter, and at the end of treatment (EOT) and end of study (EOS) visits.

8.2. Statistical Analysis Methods

Individual subject concentration for andecaliximab will be listed and summarized using descriptive statistics by treatment. Summary statistics (n, mean, StD, coefficient of variation [%CV], median, min, max, Q1, and Q3) will be presented for individual subject concentration data by time point.

Individual concentration data listings and summaries will include all subjects with concentration data. The sample size for each time point will be based on the number of subjects with non-missing concentration data at that time point. The number of subjects with concentration BLQ will be presented for each time point. For summary statistics, BLQ values will be treated as 0 at predose and one-half of the lower limit of quantitation (LLOQ) for postdose time points.

The following tables will be provided for andecaliximab:

- Individual subject concentration data and summary statistics

The following listing will be provided

- PK sampling details by subject, including procedures, differences in scheduled and actual draw times, and sample age will be provided in listings.

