5.3.1.1. Andecaliximab

If a subject experiences a Grade 3 toxicity or greater that is felt to be due to study drug andecaliximab, treatment will be postponed until the toxicity is resolved to Grade 0 or 1 (as defined by CTCAE v 4.03) or returns to the subject's baseline value. If the toxicity is resolved to Grade 0 or 1 or returns to the subject's baseline value, the subject may resume andecaliximab at the originally assigned dose level. If the subject experiences a recurrence of the Grade 3 or greater toxicity after restarting andecaliximab, treatment with andecaliximab will be discontinued.

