8.2.1.3. Pharmacodynamic and Pharmacokinetic Analysis Sets

The Pharmacodynamics and PK Analysis Sets will include data from subjects in the Safety Analysis Set who have the necessary baseline and on-study measurements to provide interpretable results for the specific parameters of interest.

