8.7. Pharmacokinetic Analysis

The plasma concentrations of andecaliximab will be summarized by nominal sampling time using descriptive statistics (eg, sample size, arithmetic mean, geometric mean, coefficient of variation (%), standard deviation, median, minimum, and maximum). Plasma concentrations of the study drug over time may be plotted in semi logarithmic and linear formats as mean \pm standard deviation.

Exposure-response analysis may be explored as appropriate.

The number and percentage of positive or negative anti-andecaliximab antibody values at each specified time-point will be summarized. The effect of anti-andecaliximab antibody on andecaliximab PK, safety, and efficacy may be evaluated.

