3.1.3. Pharmacokinetic Analysis Set

The Pharmacokinetic (PK) Analysis Set will include all randomized subjects who took at least 1 dose of andecaliximab and have at least 1 nonmissing post dose concentration value reported by the PK laboratory. This is the primary analysis set for all PK analyses.

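### The andecaliximab time-point summaries have no rule on dose given or time since last dose, so predose values after missed doses enter the trough means, and the EOT and EOS rows have no defined time since dose (minor, descriptive PK analysis)

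*SAP*

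**What the plan says.** SAP 8.2 plans descriptive statistics for andecaliximab concentration by time point. On inclusion it says "Individual concentration data listings and summaries will include all subjects with concentration data", and on the denominator "The sample size for each time point will be based on the number of subjects with non-missing concentration data at that time point". Values below the limit of quantitation count as 0 at predose and as half the lower limit at postdose (SAP 3.7 and 8.2). Differences between scheduled and actual draw times are listed.

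SAP 8.1 takes samples in Arm A after the Day 1 infusion, then before dosing and 30 (±15) minutes after infusion at Weeks 4, 8, 16 and 24, then "every 3 months thereafter, and at the end of treatment (EOT) and end of study (EOS) visits".

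The SAP 3.1.3 PK Analysis Set needs at least one andecaliximab dose and subjects who "have at least 1 nonmissing post dose concentration value reported by the PK laboratory". Protocol 8.2.1.3 instead takes subjects from the Safety Analysis Set who "have the necessary baseline and on-study measurements to provide interpretable results for the specific parameters of interest". Protocol 8.7 also uses nominal times: "The plasma concentrations of andecaliximab will be summarized by nominal sampling time using descriptive statistics".

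On dosing, Protocol 5.3.1.1 says that after a Grade 3 or higher toxicity attributed to andecaliximab, "treatment will be postponed until the toxicity is resolved to Grade 0 or 1" or returns to baseline. Protocol 3.5.1 says "Subjects enrolled on Treatment Arm A who discontinue andecaliximab for reasons other than progression may continue nivolumab", after consultation with the sponsor.

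**The concern.** A mean trough is read as the concentration at the end of a two-week dosing interval. If the dose two weeks earlier was not given, the predose sample measures something else, but the SAP puts it in the same row under the same label. Missed, postponed or stopped doses make such values lower than a true trough, so the row mean falls and the spread widens. A reader of the table cannot separate this from the drug's kinetics.

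EOT and EOS have a related problem. Each would be one row in a time-point table, yet neither visit is tied to the last andecaliximab dose.

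What is at stake is how clearly a named secondary objective is reported, namely characterising andecaliximab PK in combination with nivolumab. SAP section 1 says the synoptic CSR follows this SAP for everything except efficacy, so these summaries are what the report would carry.

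**Working it through.** The plan gives no figure on this point, so there is none to reproduce. The check has two parts: what the text admits, and how much it could matter.

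**1. Which samples enter.** The inclusion sentence in SAP 8.2 is about subjects. That every reported value enters follows from the denominator sentence (any non-missing value at the time point) together with the absence of an exclusion rule. SAP 3.1.3 is a subject-level minimum. The visit windows in SAP 3.8.2 cover laboratory tests, vital signs, ECG, ECOG and tumour assessments, but not PK.

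**2. Whether off-schedule predose samples can arise.** Andecaliximab may be postponed (Protocol 5.3.1.1), withheld separately from nivolumab (5.3.1), or stopped while nivolumab continues (3.5.1). Protocol 3.5 has a subject who stops one study medication continue the remaining regimen and the study procedures. If the Week 6 dose is missed, a Week 8 predose sample falls 4 × 7 = 28 days after the last dose.

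**3. Size, by illustration.** The documents give neither a half-life nor the share of subjects affected, so both are assumed. The model is linear, with one-compartment decline and doses every 14 days.

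- Relative trough R = [sum over doses given of 2^(-(T - t)/h)] / [the same sum over all scheduled doses], where T is the sample day, t the dose day and h the half-life in days.
- Shift of the mean = -f × (1 - R), where f is the share affected.

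Near steady state with only the last dose missed, R is close to 2^(-14/h).

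| Half-life | R, Week 24, last dose missed | Shift, f = 10% | R, Week 24, last four doses not given | Shift, f = 10% |
|---|---|---|---|---|
| 7 days | 0.25 | -7.5% | 0.004 | -10.0% |
| 14 days | 0.50 | -5.0% | 0.06 | -9.4% |
| 21 days | 0.63 | -3.7% | 0.15 | -8.5% |

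For example, at 7 days: -0.10 × (1 - 0.25) = -7.5%. With 60 subjects planned in Arm A, f = 10% is 6 subjects if all are sampled. For one missed dose, f = 5% gives -1.9% to -3.8% and f = 20% gives -7.4% to -15.0%. The shift cannot exceed f, because a value cannot fall below zero.

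At Week 4, with the Week 2 dose missed, R is 0.20, 0.33 and 0.39. The f = 10% shift is then -8.0%, -6.7% and -6.1%.

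**4. EOT and EOS.** EOT is done as soon as possible after the decision to stop all treatment (Protocol 6.5). EOS is done when a study-discontinuation criterion is met (6.6). Subjects off treatment without progression stay on study (3.6, 6.3). Relative to a 14-day trough, a sample d days after the last dose is 2^(-(d - 14)/h):

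| Half-life | 30 days | 56 days | 112 days |
|---|---|---|---|
| 7 days | 0.21 | 0.016 | 0.0001 |
| 14 days | 0.45 | 0.125 | 0.008 |
| 21 days | 0.59 | 0.25 | 0.04 |

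One EOS mean can combine values that differ by an order of magnitude or more through timing alone. The SAP also does not say whether a value below quantitation at EOT or EOS takes the predose rule (0) or the postdose rule (half the limit).

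**5. Interval compatible with the visit windows.** Protocol Appendix 2 allows ±3 days at each visit. Two consecutive compliant visits can be 14 - 6 = 8 to 14 + 6 = 20 days apart.

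**The case against.** The strongest reply is that summarising observed concentrations at nominal times is the protocol's own plan (8.7) and a legitimate as-treated description. Restricting to dose-compliant samples answers a different question, so calling the all-samples mean biased presumes one target. That stands, and it is why the all-samples table should be kept. It does not excuse leaving the target of the trough row unstated.

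The size is also entirely assumed. The protocol reports limited andecaliximab toxicity (1.3), and continuing nivolumab alone needs sponsor consultation, so 10% may be too high. Medians and quartiles are shown beside the mean, individual values are tabulated, and draw-time differences are listed. This too stands, although the listing is not stated to show missed doses or time since last dose.

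Four stronger readings are tempting, and the documents do not support them:

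- **EOT and EOS values are averaged with the scheduled troughs.** SAP 8.1 names them as their own sampling visits, and nothing pools them with Weeks 4 to 24.
- **Post-infusion rows contain samples from subjects who were not infused.** Sampling is defined relative to an infusion. The documents do not say whether a sample is drawn when none is given.
- **The SAP removed a sample-exclusion rule found in Protocol 8.2.1.3.** That section selects subjects and sets no dose-timing criterion. The two PK sets are worded differently, but no sample rule was lost.
- **The result would be misread as lower exposure in combination.** No arm receives andecaliximab alone, and no PK comparison is planned.

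**Conclusion.** The point holds as a minor, inexpensive improvement to a descriptive analysis. Followed as written, SAP 8.2 lets predose values drawn after missed, postponed or stopped andecaliximab doses into the nominal-week trough summaries, where they lower the mean. It also reports EOT and EOS as single time points with no defined time since dose.

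The direction for missed or stopped doses is downward; the amount is unknown. The illustration of -3.7% to -7.5% at Week 24 rests on assumed half-lives of 7 to 21 days, 10% of subjects missing only the preceding dose, linear kinetics, and affected subjects otherwise resembling the rest.

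A reader might infer that the PK secondary objective is biased. That goes too far: the objective is to characterise PK, with no test, parameter or decision rule attached, and no efficacy result depends on it.

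**What to change.** Amend SAP 8.2 before database finalization, or record the change in the CSR if the SAP is already final:

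- Keep all concentrations in the listings. Add days since last andecaliximab dose and a flag for missed andecaliximab doses, counting all missed doses to date.
- Restrict the main predose summary to samples drawn before dosing where the preceding scheduled andecaliximab dose was given 8 to 20 days earlier. A 14 ± 3 day rule would exclude protocol-compliant troughs.
- Restrict the main post-infusion summary to samples taken 15 to 45 minutes after the end of an andecaliximab infusion actually given at that visit.
- Present EOT and EOS concentrations by days since last andecaliximab dose, as a listing or plot, not as a nominal time-point mean.
- Keep the all-samples summary as a supporting table.

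The cost is a paragraph of SAP text, a flag derived from dosing and draw-time records, and a somewhat smaller n at some visits. One limit remains: a subject who missed several doses and resumed one dose before the sample would pass the predose rule. That is why the flag should count all missed doses.
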